Refine PATH					X							
Procedures Finalized and Staff Trained					X							
Final IRB Approval and Material Prep					X							
Assessor and Therapist Training	X				X			X				X
Recruit Participants		X	X	X	X	X	X	X	X			X

Patient Treatment	X	X	X	X	X	X	X	X	X	X
Assessment	X	X	X	X	X	X	X	X	X	X
25% Recruitment Target (n = 34)			X							
50% Recruitment Target (n = 67)					X					
75% Recruitment Target (n = 101)							X			
100% Recruitment Target (n = 135)								X		
Analyzing and Interpreting Results									X	X
Manuscript Preparation and Submission									X	X
General Grant Procedures									X	X
Research Performance Progress Reports			X			X		X		X
Data Sharing NDCT	X		X		X		X		X	X

Phone Screening. Members of the study team will collect demographic data and complete an eligibility screening form (type of destabilizing event, inclusion/exclusion criteria). Brief versions of the PSS-I and QIDS-C will be used. Potentially eligible individuals will be scheduled for an intake; those excluded will be given referrals and we will retain their demographic information and reason for exclusion for the creation of consort diagrams. All clinical data will not be utilized and ultimately deleted.

Pre-treatment Assessment. After informed consent, a study team member (licensed therapist or under the supervision of someone licensed) will administer measures of PTSD (PSS-I), depression (QIDS-C), and suicidality (C-SSRS). Assessors will be blind to treatment assignment (in R33). Patients will complete baseline self-reports and laboratory paradigms. See Figure 2.

Active Treatment. Someone on the study team (licensed or under the supervision of someone licensed) will administer the treatment sessions. In the R61, all patients will receive PATH. In the R33, patients will be randomized to PATH or PMR, using a computerized algorithm accounting for initial symptom severity.

Post-Treatment Assessment. A study team member, either someone licensed or under the supervision of a licensed therapist, will re-administer PSS-I, QIDS-C, and C-SSRS; patients will complete self-reports and tasks of target engagement. Treatment dropouts will be immediately assessed and will stay in the assessment portion of the study.

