Booster Sessions. Partial responders (less than 20% reduction on PTSD or MDD symptoms; Graham et al., 2017) to the 6 sessions of PATH or PMR will receive 2 booster sessions from members of the study team (licensed or under the supervision of someone licensed). All others will enter follow-up. This will provide **dosing and timing** information by examining how many participants respond to 6 sessions, and how many become responders with the booster sessions.

1- and 3-Month Follow-up Assessments. Patients will be re-evaluated 1 and 3 months after treatment by a member of the study team (licensed or under the supervision of someone licensed). The PSS-I, QIDS-C, and C-SSRS will be re-administered, and all self-reports and tasks of targets engagement will be completed. Additional treatment will be documented and referrals provided as needed.

Data to be Collected for your study (AFTER consent and HIPAA Authorization have been obtained)

List all data to be collected for the research study or attach a data collection sheet (e.g. laboratory values, physician notes, length of stay, etc.)

At the beginning of the intake, participants will complete the informed consent process prior to the collection of study data. After the informed consent process, information for the NIMH Data Archive GUID (full name, sex, date of birth, and city of birth) will be collected at baseline. More information about the GUID can be found in section 9 of the supplemental protocol. During intake, also after the informed consent process, a participant information and history interview, a destabilizing life event history interview, and a brief goal assessment interview will be conducted.

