Note. ¹For Go to R33, at least 2 of the 3 primary mechanism indicators must change and at least one of the secondary indicators must change. For

Second, at least one of the secondary measures must show a moderate effect ($d = 0.50$) from pre- to post-treatment. We included measures of each of the targets, as they are conceptualized as interrelated parts of a "stuck" system. For "Go" to an R01 after the R33, in addition to target engagement, primary outcomes of PTSD and depression must show clinically meaningful gains (e.g., Barth et al., 2016; Cusak et al., 2016).

R33 PATH Refinement. Beyond examining outcome data from the R61, we will: 1) conduct interviews with standardized questions with 20% of patients, selecting those with small and large gains on therapeutic targets; 2) conduct a feedback session with therapists to identify aspects of the manual that need refinement; and 3) examine booster session data regarding whether additional sessions are needed for the R33. The interview guides will be submitted as through a modification before they are conducted.

Data Analysis Plan

Directions: Describe the data analysis plan, including any statistical procedures. If applicable, provide a power analysis, describe primary and secondary study endpoints including safety endpoints.

General Analytic Strategy

For Specific Aims 1–3, we will use random effects models, a specific application of general linear mixed models (GLMMs) that helps to address common issues with longitudinal clinical treatment data, including missingness, serial correlation, and time-varying covariates (e.g., Gallop & Tasca, 2009). These models allow for person-specific deviations from overall mean time effects and are robust to missing data, using maximum likelihood estimation in cases of ignorable non-response. This analytic approach allows for initial modeling of different covariance structures, as well as non-linear time transformations that are especially useful when between-assessment intervals are not consistent across time. For Aim 3, mediation will be tested using the product of coefficients method with bootstrapped standard errors (MacKinnon, 2009) and based on a lagged mediation design (e.g., Hofmann, 2006). This approach addresses the need for temporal precedence of predictor to outcome and accounts for change between time points of a target DV. Analyses involving secondary metrics (i.e., PTCI, BADS, SHAPS) will shift to a more conservative GLM framework.

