Our approach to power analyses aims to balance pragmatic factors with analytic considerations. We focus primarily on Specific Aim 1 (R61) and Specific Aim 2 (R33). Primary analyses for both aims will involve random effects models; however, because it is difficult to accurately estimate covariance structures of such models, *a priori* power or sample size estimations have limited value. Fang (2006) has shown that ideal sample sizes often far exceed clinical resources for conventional trials, whereas other studies have shown that small sample sizes do not bias estimates of fixed effects (e.g., Bell et al., 2008). Accordingly, we frame our power calculations in line with GLM models that mirror the primary tests and hypotheses of our more complex random effects/GLMM models. In general, estimates were calculated based on $\alpha = .05$ and power $(1 - \beta) = .80$, using intent-to-treat, repeated-measures designs (e.g., paired t-tests). Power calculations were completed using G*Power (Faul et al., 2007). For Aim 1, with an estimated pre-post effect size of $d = 0.60$ (one-tailed tests), we are well-powered with a sample of 45. In fact, for a sample size of 45, an alpha of .05, and power of .80, we will be able to detect a small to moderate effect size of .38. For Aim 2, we based power estimates on a primary comparison of time by treatment interaction in an RMANOVA model. For a five time points, two groups, RMANOVA with a correlation of $r = .70$

between measures, we are well powered to detect treatment X time small effect size of .07 with 67 patients per treatment. For Specific Aim 3, using Monte Carlo simulations in MPlus 6.0 (Muthen & Muthen, 2002) with the same alpha, power, and sample size of at least 67 per condition, we are adequately powered to detect an indirect effect size as small as $d = .50$.

Specific Aim 1: Engage Targets (R61)

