Participants will be instructed that information shared in sessions is confidential. Participants will be instructed about the limitations and obligations in regard to reporting of elder abuse, child abuse, suicidality and homicidality. We will follow state laws and professional ethics in handling these issues. Participants will be reminded at each appointment that they do not need to disclose any information that they are not comfortable with sharing. Participants will be given the phone number for Case Western staff and will be given the Cuyahoga County 24-hour crisis [contact].

Potential Benefit to Research Participants

Describe the potential benefits that individual research participants may experience from taking part in the research. Include the probability, magnitude, and duration of the potential benefits. If there is no direct benefit, state the potential benefit to society.

We anticipate that receiving PATH will lead to improvements in functioning for participants, including reduced symptoms of PTSD, depression, and functioning. However, this cannot be guaranteed.

Withdrawal of Research Participants

Directions: Describe the anticipated circumstances under which research participants will be withdrawn from the research without their consent. Also include the procedures that will be followed when a research participant withdraws or are withdrawn from the research, including partial withdrawal from procedures with continued data collection.

At every session, patients will be clinically monitored for suicidal risk or serious depression, and withdrawn from the study if these conditions are present and preclude participation. If research participants choose to withdraw from the study, they will do so by contacting the local investigator ([name]).

Alternatives to Participation

Directions: List other available clinical treatments, what would be included if a subject continued on standard of care therapy. If this is not a clinical trial, you may select the box indicating that the alternative is not to participate. If there is a viable alternative you must list it in the consent.

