Non-response and relapse of responders are possibilities. Throughout the course of the study, patients' current symptoms, including suicidality, will be carefully assessed. Before every treatment session and at every assessment, patients will complete self-report ratings of their PTSD (PDS-5) and depression (QIDS-SR). The treatment provider (PATH or PMR) at the start of the session will review symptom ratings. For those with suicidal risk or serious depression, patients will be withdrawn from the study if these conditions are present and preclude participation. If a clinician is concerned about the level of a client's suicide risk based on client verbalization or QIDS-SR, the session will focus on risk assessment and management. If necessary, procedures are in place for imminent at risk patients to be escorted to local emergency rooms. If a patient calls their treatment provider or the research coordinator in crisis, an emergency session will be scheduled immediately. All concerns about suicide risk will be brought to the attention of the PIs (licensed clinical psychologists) immediately. All patients will be given 24-hour suicide prevention hotline numbers at the beginning of the trial and reminded of this on as needed basis. In addition, patients will have access to the emergency rooms at University Hospital of Cleveland (UHC, CASE's affiliate), Wilmington Hospital and Christiana Care Hospital in Delaware, and at UW Medical Center, and to study clinicians within 24 hours. Finally, built into the protocol is the provision of up to two Adjunctive Services and Attrition Prevention (ASAP) sessions to address emergent clinical issues. In our prior trials, we have not needed to exceed the provision of two ASAP sessions. Taken together, we have used these procedures successfully for the past decade in our previous trials to manage risk successfully. Non-responders will be offered continued treatment, as outlined in Approach Section, free of charge or various referral options. Relapsed patients in the follow-up phase will be offered additional treatment sessions or various referral options. The referral options include treatment through outpatient psychiatry at CASE, UD (Wilmington Hospital, Christiana Care Hospital), or UW.

Community-Based Participatory Research

Describe the involvement of the community in the design and conduct of the research.

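### Safety withdrawal is written as leaving the study, and the rule that keeps dropouts in assessment does not reach patients withdrawn after four or more sessions

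*Combined protocol and SAP*

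**What the plan says.** Two places in the combined protocol and SAP state the withdrawal rule. Withdrawal of Research Participants sets a check for each visit: "patients will be clinically monitored for suicidal risk or serious depression, and withdrawn from the study if these conditions are present and preclude participation". Additional Information says that "patients will be withdrawn from the study if these conditions are present and preclude participation".

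The template prompt above the first statement asks for withdrawal procedures, "including partial withdrawal from procedures with continued data collection". The reply does not take up that part.

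The Post-Treatment Assessment paragraph (under Study Timeline) has a retention rule: "Treatment dropouts will be immediately assessed and will stay in the assessment portion of the study". Treatment Engagement, Acceptability, and Feasibility defines treatment dropout as fewer than four completed sessions and attaches no reason. At the 1- and 3-month follow-ups, "The PSS-I, QIDS-C, and C-SSRS will be re-administered, and all self-reports and tasks of targets engagement will be completed".

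Additional Information also describes responses short of withdrawal. Where a clinician is concerned about suicide risk, "the session will focus on risk assessment and management". Emergency sessions and up to two adjunctive sessions are available as well.

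**The concern.** The reason for withdrawal overlaps an outcome. Under Milestones (Go/No Go Criteria), going on to an R01 requires that "primary outcomes of PTSD and depression must show clinically meaningful gains", and Table 3 sets d >= 0.80 on the depression interview. If leaving the study means leaving the assessments, patients removed for serious depression supply no later QIDS-C, and the means are computed without some of the worst-off patients.

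The mixed models in General Analytic Strategy rely on maximum likelihood with ignorable non-response, and this mechanism strains that assumption. Power Analysis names intent-to-treat designs, which fits continued assessment. Aim 3 needs pre-to-post change in the targets and symptoms at follow-up, and a patient withdrawn before post-treatment would supply neither. These patients would also miss the routine ideation checks at follow-up. Three sites could in good faith apply the wording differently.

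**Working it through.** **Whom the two rules reach.** The five time points (Data to be Collected) are pre-treatment, after session 3, post-treatment, 1 month and 3 months. Post-treatment is taken to precede the boosters, as the order of the text implies.

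| When the team withdraws the patient | Meets the dropout definition? | Time points lost, read literally |
|---|---|---|
| Before the after-session-3 assessment | Yes | 4 of 5 |
| After that assessment, fewer than four sessions completed | Yes | 3 of 5 |
| Four or more sessions completed, before post-treatment | No | 3 of 5 |
| At a booster | No | 2 of 5 |

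In the first two rows the retention rule arguably applies but conflicts with withdrawal from the study. In the last two rows it does not apply, and nothing in the supplied text replaces it.

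**Size in the R33 PATH arm, QIDS-C.** The plan gives no figure to reproduce, so this is an illustration.

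- From Power Analysis: 67 patients per arm and correlation r = .70 between measures, here taken as equal across all time points.
- Assumed: k = 1 to 4 patients withdrawn, each D = 1.0 SD worse at follow-up and average at pre-treatment.
- Formula: shift in mean = (k/N) x D x share not recovered by the model.
- Deficit not yet visible in any observed value: share = 1.0. Shift = 1/67 = 0.015 to 4/67 = 0.060 SD.
- Deficit already visible after session 3: recovered weight = .70/(1 + .70) = 0.412, share = 0.588. Shift = 0.015 x 0.588 = 0.009 to 0.060 x 0.588 = 0.035 SD.
- With D from 0.5 to 1.5 SD: from 1/67 x 0.5 x 0.588 = 0.004 to 4/67 x 1.5 = 0.090 SD.

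A simulation with k = 4 and D = 1.0 (20,000 runs) gave 0.035 and 0.060 SD, in agreement.

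**Between-arm contrast.** Equal rates and severity give 0. With 3 versus 1 withdrawn of 67 per arm, the shift is 2/67 = 0.030 SD, or 0.030 x 0.588 = 0.018 SD if the after-session-3 value shows the deficit.

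**R61 self-report targets (N = 45, threshold d = 0.50).** The same formula gives 1/45 = 0.022 to 4/45 = 0.089 SD with nothing recovered. PTCI, BADS and SHAPS are taken at every session. A patient stopped after session 4 has five observed values, each weighted .70/(1 + 4 x .70) = 0.184. If those values are modelled, 0.18 SD (deficit at the last session only) to 0.74 SD (deficit at all four sessions) of D is recovered. The shift is then between 0.022 x 0.26 = 0.006 and 0.089 x 0.82 = 0.073 SD. The plan moves these measures to a GLM, which may not use the session data.

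**Precision.** A paired one-sided test with n = 45 gives a detectable d of 0.376, matching the stated .38. For R33, the repeated-measures noncentrality f^2 x N x 5/(1 - .70) with N = 134 gives a detectable f of 0.073, which rounds to the stated .07. An assumed 2% to 10% loss moves these to 0.381 to 0.400 and 0.074 to 0.078. The loss of precision is small, so the issue is which patients go missing.

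**The case against.** Read with the dropout definition, the retention rule already covers a patient stopped before completing four sessions. This stands as a fair reading and narrows the gap to later withdrawals, though the conflicting wording remains.

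The withdrawal rule is conditional: the condition must preclude participation, other responses come first, and high-risk patients are excluded at entry. Few withdrawals are likely. Some of those withdrawn could not safely be assessed in any case.

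Much of the severity behind a withdrawal is recorded. PDS-5 and QIDS-SR are completed before every session and could inform the planned pattern-mixture checks and multiple imputation. This mitigates the problem, but imputation cannot replace observed follow-up, and the plan does not say how much worse such patients are assumed to fare.

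The document also refers to a supplemental protocol and an Approach Section that are not supplied. The absence of a rule can be claimed only for the text at hand.

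A reader might infer that every patient with suicidal risk leaves the trial, or that withdrawal ends safety care. Neither follows. Emergency care, referral and reporting of serious adverse events do not depend on this rule; what may be lost is the routine follow-up check of ideation. Nor does the expected dropout below 20% (Specific Aim 4) cap these withdrawals, because it concerns patients with fewer than four sessions.

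**Conclusion.** The point holds as a minor one. The written rule, taken literally, ends outcome assessment for patients removed because of suicidal risk or serious depression, and no supplied text overrides it once four sessions are complete. The likely bias is small: about 0.01 to 0.06 SD in the R33 PATH-arm QIDS-C mean, and near 0 between arms if withdrawals are balanced. These figures rest on an assumed number of withdrawals, an assumed deficit and the plan's r = .70. The true bias cannot be estimated, because no withdrawal rate is given.

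A reader might conclude that the main results or a Go decision are compromised. The documents do not support that. The primary measures for Aims 1 and 2 are laboratory tasks, for which the shift may be zero, and no threshold is shown to be crossed. The case for acting is that the lost data cannot be recovered later and are cheap to keep.

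**What to change.** In Withdrawal of Research Participants and in Additional Information, state that safety withdrawal stops study treatment. Add that the retention rule in the Post-Treatment Assessment paragraph then applies whatever the number of sessions completed. These patients are assessed promptly and stay in the scheduled post-treatment, 1-month and 3-month assessments, with C-SSRS, PSS-I and QIDS-C as the minimum, unless they withdraw consent or assessment is clinically inadvisable. State that their data enter the analyses. When treatment should stop remains the investigators' decision.

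The cost is a wording change in two places, and in the consent form if it repeats the rule. The assessments are already scheduled and compensated, and are currently done remotely. Some patients may find the visits burdensome, decline them, or be unable to do the tasks, especially the behavioral approach task; interviews alone would still keep the clinical outcomes.

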The Perceived Stress Scale (PSS; Cohen, Kamarck & Mermelstein, 1983) is a 10-item self-report measure that assesses participants’ self-perception of stress in their lives. More specifically, the PSS measures the extent to which participants think their lives are unpredictable, uncontrollable, and overloaded. Items are rated on a Likert scale ranging from 0 (*never*) to 4 (*very often*). Total scores range from 0 to 40, with higher scores indicating higher levels of perceived stress.

The Working Alliance Questionnaire (WAQ; Falkenström, 2015) is a 6-item self-report measure assessing the participants’ thoughts and feelings about the relationship with their therapist. Items are rated on a 6-point Likert scale from 0 (not at all) to 5 (completely). Total scores range from 0 to 30 with higher score indicating higher working alliance.

The EDS-R and PEIS will be given at the pre- and post-treatment assessments. The PSS will be given at pre-treatment, mid-treatment, and post-treatment. As noted, the Hassles and Uplifts Scale will be given daily for one week pre-treatment, one week mid-treatment, and one week post-treatment.

Psychopathology Symptom Measures

Both PTSD and depression will be assessed with state-of-the-art, psychometrically-validated interview and self-report measures (PTSD Symptom Scale-Interview, PSS-I-5; PTSD Diagnostic Scale, PDS-5; Foa et al., 2015; Quick Inventory of Depressive Symptomatology-C, QIDS-C; Quick Inventory of Depressive Symptomatology-SR, QIDS-SR; Rush et al., 2003). The Structured Clinical Interview for DSM-5 (SCID-5-RV; First et al., 2015) and the Columbia-Suicide Severity Rating Scale (C-SSRS; Posner et al., 2009) will be administered by members of the study team (licensed or under the supervision of a licensed therapist) used to assess inclusion/exclusion criteria and monitor suicidality.

Positive and Negative Affect Scale (PANAS; Watson et al., 1988) will be used to assess state affect across assessments and sessions, particularly for examining dose and timing of PATH in Specific Aim 1.

Response to Positive Affect – Dampening Subscale (RPA-D, Feldman et al., 2008) is an 8-item self-report measure assessing dampening responses to positive affect states. Respondents rate the items on a 4-point Likert scale, ranging from 1 (almost never) to 4 (almost always).

All self-report psychopathology symptom measures will be given at each assessment point and at each session.

Treatment Engagement, Acceptability, and Feasibility

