We will examine whether PATH alters therapeutic targets in comparison to PMR. Primary dependent variables are Affective Updating, BATs, PRT. Secondary dependent variables are PTCI, BADS, and SHAPS. We will compare the main effect of treatment (PATH or PMR) over time separately in each of three models. These models will estimate the effects of treatment on both the level of the target at 3-month follow-up and change over time (slope). Random intercepts and random coefficients for time-varying covariates (e.g., time) will be specified, if the model fit is better than a fixed effects model. For example, $y_{ik} = \beta_0 + \beta_1 \text{Time}_{ik} + \beta_2 \text{Treatment}_{ik} + \beta_3 (\text{Treatment}_{ik} \times \text{Time}_{ik}) + v_{0i} + v_{1i} \text{Time}_{ik} + \epsilon_{ik}$ where Treatment represents a dummy-coded effect (Group = 0 for PATH, 1 for PMR), i=subject, k=time, and y = DV of interest. We hypothesize that differences will emerge between PATH and PMR specifically for Affect Updating, BAT, and PRT. For secondary measures, we will use the GLM approach above in an ANCOVA-like design to test the interaction of treatment and time.

Specific Aim 3: Linking Changes in Targets to Changes in Stressor-related Symptoms (R33):

We will examine whether changes in target mechanisms (pre- to post-) predict improvement in PTSD (PSS-I) and depression (QIDS-C) at pre-, mid, post-, 1-, 3-month follow-up. In GLMs, we will evaluate targets from pre- to post-treatment and at 3-month follow-up, with corresponding metrics to assess change in symptoms (PSS-I, QIDS-C). In the GLMs, treatment will predict changes in symptoms from pre- to post-treatment (controlling for baseline levels) and pre- to follow-up. GLMMs will be conducted as above, and treatment will be used to predict levels and change in symptoms. Next, in GLMs, we will

predict pre-post change in target mediators (unproductive processing, avoidance, reward deficits) from treatment (A path) and follow-up outcomes from the mediator (B path), controlling for treatment and baseline symptoms. GLMM will test for mediation by predicting the mediator at all time points from treatment, and the outcome at all time points from the mediator, controlling for treatment. Similar analyses will be used for secondary measures.

Specific Aim 4: Feasibility and Dropout/Acceptability of PATH Intervention (R61/R33):

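### Session-level QIDS-SR and PDS-5 ratings are collected in both arms, and QIDS-SR can inform withdrawal, but neither scale is named in any outcome or imputation model, so improvement in PSS-I and QIDS-C may be somewhat overstated

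*Combined protocol and SAP*

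**What the plan says.** **Collection.** Additional Information: "Before every treatment session and at every assessment, patients will complete self-report ratings of their PTSD (PDS-5) and depression (QIDS-SR". Psychopathology Symptom Measures agrees: "All self-report psychopathology symptom measures will be given at each assessment point and at each session". The treating provider, PATH or PMR, looks at the scores when the session starts, and the QIDS-SR is singled out as the tool for watching suicide risk during treatment.

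**Withdrawal.** Additional Information: "For those with suicidal risk or serious depression, patients will be withdrawn from the study if these conditions are present and preclude participation". Withdrawal of Research Participants says much the same: "At every session, patients will be clinically monitored for suicidal risk or serious depression, and withdrawn from the study if these conditions are present". No score cut-off is given. A concern about "suicide risk based on client verbalization or QIDS-SR, the session will focus on risk assessment and management".

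**Dropouts.** The post-treatment paragraph under Study Timeline: "Treatment dropouts will be immediately assessed and will stay in the assessment portion of the study". Whether this covers patients withdrawn from the study, as opposed to from treatment, is not stated.

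**Analysis.** General Analytic Strategy says the mixed models "are robust to missing data, using maximum likelihood estimation in cases of ignorable non-response". The same section plans pattern-mixture models to examine ignorability, and multiple imputation where it fails, without listing the imputation variables. Specific Aim 3 asks whether target changes "predict improvement in PTSD (PSS-I) and depression (QIDS-C) at pre-, mid, post-, 1-, 3-month follow-up". PDS-5 and QIDS-SR do not appear anywhere in the Data Analysis Plan. Table 3 sets d of at least 0.80 on the PSS-I and the QIDS interview for the R33.

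**The concern.** A likelihood analysis can ignore the missing-data mechanism when loss depends only on values that are in the model. Here, part of what can lead to loss is on file but outside the model. The mid-treatment interview follows session 3. For someone withdrawn after session 5, the most recent information is the QIDS-SR from the later sessions. A model built on PSS-I and QIDS-C alone predicts that patient's later scores from the pre and mid interviews. If the later ratings had worsened, the prediction is too favourable.

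The direct exposure is the improvement within each arm, including the d of at least 0.80 in Table 3, where nothing cancels. The PATH versus PMR contrast is exposed only to the extent that loss, or its relation to the ratings, differs by arm. The imputation fallback does not help by itself, because imputing from the same interview scores repeats the same prediction.

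**Working it through.** **The plan's own figures.** The documents give no rate of study withdrawal and no missing-data or bias figure, so there is nothing to reproduce. The nearest number, dropout below 20% under Specific Aim 4, concerns treatment dropout (fewer than 4 sessions).

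**Set-up (all inputs assumed).** One arm, 1,000,000 simulated patients, standard normal scores with true mean 0. Pre, mid, post and 3-month interview scores correlate at r = 0.5 or 0.7. A session rating taken after mid-treatment correlates r with pre, mid and 3-month and 0.8 with post. A share w is withdrawn because of that rating, either by a sharp threshold or with graded (logistic) probability.

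**Estimator.** Among patients still observed, regress the 3-month score Y on pre and mid, then predict Y for those withdrawn:

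estimated mean = (1/N) × [sum of observed Y + sum of (b0 + b1·pre + b2·mid) over withdrawn patients].

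The bias is this estimate minus 0. A negative value means improvement is overstated.

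**Check of the set-up.** For completers only with a sharp threshold, theory gives a bias of −r·φ(z)/(1 − w). At w = 0.20, z = 0.842 and φ(z) = 0.280, so φ(z)/(1 − w) = 0.350. This gives −0.175 for r = 0.5 and −0.245 for r = 0.7. The simulation gave −0.176 and −0.245.

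**Results.** Bias in the 3-month mean, in SD, shown as threshold / graded:

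| r | w | Pre and mid interviews | Plus an immediate assessment at withdrawal |
|---|---|---|---|
| 0.5 | 2% | −0.010 / −0.005 | −0.003 / −0.003 |
| 0.5 | 5% | −0.020 / −0.012 | −0.007 / −0.004 |
| 0.5 | 10% | −0.037 / −0.026 | −0.011 / −0.006 |
| 0.5 | 20% | −0.067 / −0.045 | −0.026 / −0.015 |
| 0.7 | 2% | −0.009 / −0.004 | −0.003 / −0.003 |
| 0.7 | 5% | −0.016 / −0.011 | −0.007 / −0.004 |
| 0.7 | 10% | −0.032 / −0.018 | −0.015 / −0.010 |
| 0.7 | 20% | −0.058 / −0.038 | −0.030 / −0.021 |

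With the session rating added to pre and mid, the bias is at most 0.002 SD in size in every row. Simulation error is about 1/√1,000,000 = 0.001 SD, so the smallest entries are close to noise.

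**Stronger assumptions.** A second simulation used six session ratings, loss at sessions 2 to 6 above a threshold, a pre to 3-month correlation of about 0.5, and a last-rating to 3-month correlation of 0.70 to 0.73. With 16 to 22% loss under the same rule in both arms, it gave 0.08 to 0.12 baseline SD per arm and about 0.02 SD in the contrast. Where the last rating added little to baseline, this fell to 0.02 to 0.05 SD per arm and about 0.01 SD in the contrast.

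**Contrast between arms.** Equal loss and an equal mechanism largely cancel. As an unequal example from the table (r = 0.5, threshold), 20% against 5% gives 0.067 − 0.020 = 0.047 SD. The second simulation gave 0.07 to 0.11 SD for splits of about 21% v 7% or 5% v 27%, against an assumed true difference of 0.50 SD. No document supports any particular split.

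**Against the 0.80 criterion.** 0.02/0.80 = 2.5%; 0.067/0.80 = 8%; 0.12/0.80 = 15%. This is only a guide. The figures are for the 3-month mean, whereas Table 3 labels its criterion pre-post. The post-treatment mean was not simulated. Since the assumed correlation of the rating with the post score is higher (0.8), the bias there could be larger if no post assessment is obtained.

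**The case against.** The case on the other side is substantial, and most of it stands.

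- **The plan does not claim ignorability.** A reader might infer that it wrongly asserts ignorable missingness. It does not: maximum likelihood is tied to cases where non-response is ignorable, with a check and a fallback. Nothing bars the session ratings from the imputation; the plan simply does not list its variables.
- **The ratings do not mechanically decide withdrawal.** The rule is a clinical judgment with no cut-off. A QIDS-SR concern leads first to risk assessment within the session, and what the patient says counts too. PTSD severity is not a criterion, so the documents do not support reading PDS-5 as a driver of withdrawal. A simulation in which the rating alone causes loss shows the fix at its best.
- **Treatment dropouts stay in assessment.** For them, prediction from pre and mid alone would be the wrong picture. If withdrawn patients also receive the immediate assessment, the bias is 0.03 SD or less in the table.
- **The loss rates are assumed.** At 2 to 5% withdrawal the effect is small.

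Two replies remain. The dropout sentence concerns treatment dropouts, while the withdrawal text removes patients from the study, and the documents do not say whether assessment then continues. Pattern-mixture models cannot establish from observed data that missingness is ignorable, and standard multiple imputation itself assumes missing at random given the variables supplied. The choice of those variables therefore matters.

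**Conclusion.** The concern holds in a limited form. Scores that can inform withdrawal are collected in both arms, and no analysis is told to use them. Missing-at-random is therefore less plausible than it could be for withdrawn patients, and improvement in PSS-I and QIDS-C may be somewhat overstated.

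For the 3-month mean, the size per arm is about 0.004 to 0.07 SD at 2 to 20% withdrawal. It is at most about 0.02 SD at 2 to 5%, and reaches about 0.12 SD only under the stronger assumptions. It largely cancels in PATH versus PMR unless loss differs by arm. These figures rest on assumed withdrawal rates and correlations and on loss caused by the rating.

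A reader might go further and conclude that the 3-month results are biased. The documents do not support that. It depends on how many patients are withdrawn, whether they are still assessed, how loss splits by arm, and what the ratings add to the interviews, and none of these is stated. The case for acting is that a better-supported analysis is available from data already being collected.

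**What to change.** In General Analytic Strategy, name the session-level QIDS-SR and PDS-5 scores, with those from each assessment, as auxiliary variables in the multiple-imputation model for PSS-I and QIDS-C. Alternatively, model them jointly as outcomes in the likelihood analysis. PDS-5 belongs there because it may help predict PSS-I, although it is not a withdrawal criterion. Extending this to the target measures is optional; no size was worked out for them. Do not enter the ratings as covariates in the treatment-effect model, because they are measured after randomisation. Keep the PATH versus PMR contrasts as planned.

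The text should also state whether patients withdrawn from the study continue to be assessed, and the report should give withdrawals by arm and reason.

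The cost is a change of wording and a larger model, with no new data collection. In the second simulation (1,500 trials of 135 patients) the sampling SD of the estimate rose by about 2% or less. The change should reduce the bias but does not guarantee its removal, because withdrawal may also depend on clinical judgment that is not recorded as a score.
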